To investigate the feasibility and acceptability of a novel MI-based telehealth intervention to engage GBMSM-LWH in GC, CT, and syphilis testing, we propose to conduct a 2-year sequential explanatory mixed-methods study. 70, 71 Our intervention is a package of 3 components: (i) a pretest live AV conferencing session involving an MI-guided discussion to elicit awareness of bacterial STIs and fill any knowledge gaps, bolster the perceived importance of regularly testing for GC, CT, and syphilis, and improve self-efficacy for specimen self-collection, (ii) self-collecting at home and returning by mail a urine sample (for GC and CT testing), a throat swab (for GC and CT testing), arectal swab (for GC and CT testing), and a finger-stick blood sample (for syphilis testing), and (iii) a post-test live AV conferencing session involving an MI-guided discussion to prepare participants for receiving test results and formulate personalized action plans for seeking treatment (if warranted) and repeat testing. Feasibility will be assessed by documenting participants' levels of engagement in the pre-test session, specimen return for bacterial STI testing, and the post-test session. Acceptability will be assessed by documenting overall intervention satisfaction, interventionist perceptions, usability of the pre-test and the post-test

sessions, willingness to repeat the intervention, and likelihood of recommending the intervention to friends or sex partners. Potential increases in participants' knowledge of GC, CT, and syphilis will be assessed by comparing their responses to the same set of questions on these STIs included in the baseline survey (to be administered before intervention delivery) and the satisfaction survey (to be administered after intervention delivery). Potential increases in participants' self-efficacy for specimen self-collection will be assessed by comparing their responses to similar sets of questions on the ease or difficulty of self-collecting each specimen in the baseline survey and the satisfaction survey.

Section 5.a: We have made minor revisions to the description of outcome measures in the data analyses section to clarify which outcomes are primary and which outcomes are secondary, in alignment with the information registered on ClinicalTrials.gov. The amended text reads as follows:

Descriptive statistics (e.g., means, medians and ranges for continuous variables, counts and proportions for categorical variables) and progression ratios (i.e., proportions who sequentially progress through different intervention components) will be calculated using software for quantitative data analysis (e.g., SAS, Excel).

Primary outcome measures:

Outcomes to measure the feasibility of our intervention include the following:

- (i) Number of participants that schedule a pre-test session.
- (ii) Number of participants that join the pre-test session within 30 min of the start time.
- (iii) Number of participants that return each type of specimen within 6 weeks of box delivery.
- (iv) Number of participants that provide specimens of adequate quality for lab testing.
- (v) Number of participants that schedule a post-test session.
- (vi) Number of participants that join the post-test session within 30 min of the start time.

Outcomes to measure the acceptability of our intervention include the following:

- (i) Overall intervention satisfaction: Participants' satisfaction with the pre-test session, urine sample self-collection, throat swab self-collection, rectal swab self-collection, finger-stick blood sample self-collection, and the post-test session will be assessed using six 5-point Likert items included in the satisfaction survey. Response values will be summed to obtain a total score ranging from 6-30, with higher scores indicating greater overall intervention satisfaction.
- (ii) Interventionist perceptions: Participants' perceptions of the interventionist conducting the pretest and the post-test sessions will be assessed using two 12-item Counselor Rating Form Short scales included in the satisfaction survey. Response values will be summed to obtain a total score ranging from 24-168, with higher scores indicating more positive interventionist perceptions.
- (iii) Usability of the pre-test and the post-test sessions: Participants' usability of the pre-test and the post-test sessions will be assessed using two 4-item subscales from the Telehealth Usability Questionnaire on the quality of interactions with the interventionist during each session included in the satisfaction survey. Response values will be summed to obtain a total score ranging from 8-56, with higher scores indicating greater usability of the pre-test and the post-test sessions.
- (iv) Willingness to repeat the intervention: Participants' willingness to repeat the pre-test session, urine sample self-collection, throat swab self-collection, rectal swab self-collection, finger-stick blood sample self-collection, and the post-test session will be assessed using six 5-point Likert items included in the satisfaction survey. Response values will be summed to obtain a total score ranging from 6-30, with higher scores indicating greater willingness to repeat the intervention.

(v) Likelihood of recommending the intervention to friends or sex partners: Participants' likelihood of recommending the pre-test session, urine sample self-collection, throat swab self-collection, rectal swab self-collection, finger-stick blood sample self-collection, and the post-test session to friends or sex partners will be assessed using six 5-point Likert items included in the satisfaction survey. Response values will be summed to obtain a total score ranging from 6-30, with higher scores indicating greater likelihood of recommending the intervention to friends or sex partners.

Secondary outcome measures:

Outcomes to measure the potential impact of our intervention on IMB model constructs include the following:

- (i) Improvement in STI-related knowledge: Potential increases in participants' knowledge of GC, CT, and syphilis will be assessed by comparing responses to the same set of 22 items included in the baseline survey and the satisfaction survey. Response values will be summed to obtain separate total scores ranging from 0-22, with higher scores indicating greater STI-related knowledge.
- (ii) Likelihood of testing for bacterial STIs at least annually: Participants' likelihood of testing for bacterial STIs at least annually will be assessed using a single 5-point Likert item included in the satisfaction survey. Response values will range from 1-5, with higher values indicating greater likelihood of testing for bacterial sexually transmitted infections at least annually.
- (iii) Improvement in self-efficacy for specimen self-collection: Potential increases in participants' self-efficacy for urine sample self-collection, throat swab self-collection, rectal swab self-collection, and finger-stick blood sample self-collection will be assessed by comparing responses to similar sets of four 5-point Likert items included in the baseline survey and the satisfaction survey. Response values will be summed to obtain separate total scores ranging from 4-20, with higher scores indicating greater self-efficacy for specimen self-collection.

Outcomes to measure the prevalence of bacterial STIs and receipt of treatment include the following:

- (i) Number of participants that test negative or positive for GC, CT, and syphilis (using our specimen self-collection kits or with their own provider or at a clinic).
- (ii) Number of participants that initiate treatment (with their own provider or at a clinic or via commercial telehealth services) within 1 week of receiving a positive test result.

Because our study is inherently exploratory, we do not plan on using probability-based statistical inference techniques in line with current best practices. ^{109, 110} Instead, potential variations in our intervention's feasibility and acceptability across selected participant characteristics, and its potential impact on IMB model constructs will be numerically summarized and graphically visualized (e.g., side-by-side boxplots, scatter plots), as recommended for exploratory data. ^{111, 112}

Ame00145753

Instead of using a bubble mailer for participants to return their specimens, we will be using a shipping box made of cardboard as the outer shipping package. This change is to promote compliance with the Hazardous Materials Regulations for the safe transportation of hazardous materials, including Category B infectious substances, that recommend the use of "rigid outer packaging" (HMR; 49 CFR §173.199). To reflect this change, we have replaced the phrase "bubble mailer" with "shipping box" in the informed consent form and have updated the general information sheet that includes packaging instructions for participants. We have also included our contact details in the general information sheet and the supplemental information sheet so that

participants can readily contact us via phone or email if they have any questions. We have updated the lab test results form to include the Emory University Clinical Virology Research Lab's CLIA ID (11D1069803), so that participants can look up detailed information about the lab on the Centers for Medicare & Medicaid Services website. We have also changed the study's start date from 11/1/23 to 3/1/24. Per our correspondence with HSIP, we have checked the option for cash and unchecked the option for HSIP issued gift cards to disburse participant incentives. Study team members who have taken the TME103 training may pick up cash in the form of a prepaid Visa card from Wolverine Tower and use it to purchase e-gift cards from Amazon, which is an approved third-party vendor for HSIP.

Ame00147334

In an effort to reach a greater number of potential participants, we will also place advertisements on Adam4Adam, Jack'd, and Sniffies. We have added their Web addresses (URLs) to the application. Our advertisements will include content that has been previously approved by the IRB. We have also checked the option for Study Coordinator/Research Assistant in the fields for who will provide study information and instructions to the participants beyond what is included in the informed consent form, obtain informed consent, and monitor subjects and identify adverse events. Additionally, we have added the names and areas of expertise of the Data and Safety Monitoring Board (DSMB) members and uploaded a copy of the signed DSMB charter.

Ame00147802

To minimize the potential for fraudulent activity, we will schedule a 10 min live audio/video conferencing session over Zoom to verify a potential participant's contact information. Time slots will be offered in all US time zones and be flexible to meet their individual circumstances. Once a time is confirmed, potential participants will be sent a password-protected Zoom link. They will need to keep their camera on during the session, but no audio or video will be recorded. During the session, a study team member will verify their full name, email address, mobile phone number, and mailing address. Based on a review of the baseline and satisfaction survey metadata in Qualtrics, we will undertake a similar verification process before disbursing participant incentives on as as-needed basis. To reflect these changes, we have added this information to the informed consent form, created a new Qualtrics survey to seek re-consent, and drafted correspondence scripts for scheduling a Zoom session and for re-consenting previously enrolled participants.

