- (v) Perceived risk of bacterial STIs: Risk perception ruler from 1 (Extremely unlikely) to 10 (Extremely likely) to assess the participant's perceived likelihood of contracting a bacterial STI in the next 12 months. 98
- (vi) "Safer" sex self-efficacy: 7-item scale to assess the participant's confidence in practicing "safer" sex. 100
- (vii) Specimen self-collection self-efficacy: 5-point Likert items to assess the participant's perceived ease of self-collecting each type of specimen.
- (viii) History of HIV testing and management: Timing of first positive HIV test, location of test, receipt of HIV medical care, ART use, HIV viral load, and CD4 count.^{97, 101-103}
- (ix) History of bacterial STI testing and management: Frequency of testing for GC, CT, and syphilis, timing of latest tests, location of latest tests, types of specimens provided, test results, and receipt of treatment.
- (x) Relationship and partner characteristics: Relationship duration and type, partner's HIV status and use of ART or pre-exposure prophylaxis (PrEP), and partner's history of testing for GC, CT, and syphilis.

- (xi) Sexual behaviors: Engagement in oral, anal, and vaginal or frontal sex in the past 12 months, and condom use.
- (xii) History of substance use: Tobacco, alcohol, prescription medication, and other substance use using NIDA's TAPS screening tool. 104

The baseline survey should take approximately 1 hour to complete, and it will allow participants to skip questions or indicate that they prefer not to answer a question. If participants do not complete the baseline survey within 1 week, up to 7 reminders will be sent at regular intervals over the next 7 weeks. The reminders will inform participants that non-completion of the baseline survey by the end of 8 weeks suggests that they are no longer interested and that they will not be able to proceed in the study after that time has elapsed (unless they request an extension). Participants who do not complete the baseline survey by the end of 8 weeks will be excluded from further consideration and their personally identifiable information will be deleted within 4 weeks. Those who complete the baseline survey will receive a \$40 Amazon e-gift card and be considered "fully enrolled" participants (i.e., they will proceed to receive the intervention).

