Upon completion of the intervention delivery, all 75 "fully enrolled" participants (regardless of their level of engagement in the pre-test session, specimen return for bacterial STI testing, and the post-test session) will be sent a link to the satisfaction survey programmed in Qualtrics (with the participant ID number included as a metadata element) that will include questions on the following:

- (i) Pre-test live AV conferencing session experience: 4-item subscale from the Telehealth Usability Questionnaire to assess the participant's quality of interaction with the interventionist, 106 12-item Counselor Rating Form Short to assess the participant's perceptions of the interventionist, 107 5-point Likert items to assess the participant's satisfaction with, willingness to repeat, and likelihood to recommend the session.
- (ii) Urine sample self-collection experience: 5-point Likert items to assess the participant's experience with, willingness to repeat, and likelihood to recommend self-collection. 66
- (iii) Throat swab self-collection experience: 5-point Likert items to assess the participant's experience with, willingness to repeat, and likelihood to recommend self-collection. 66
- (iv) Rectal swab self-collection experience: 5-point Likert items to assess the participant's experience with, willingness to repeat, and likelihood to recommend self-collection. 66
- (v) Finger-stick blood sample self-collection experience: 5-point Likert items to assess the participant's experience with, willingness to repeat, and likelihood to recommend selfcollection.⁶⁶
- (vi) Specimen packaging and return experience: 5-point Likert items to assess the participant's experience with packaging and returning specimens.
- (vii) Post-test live AV conferencing session experience: 4-item subscale from the Telehealth Usability Questionnaire to assess the participant's quality of interaction with the interventionist, 106 12-item Counselor Rating Form Short to assess the participant's perceptions of the interventionist, 107 5-point Likert items to assess the participant's satisfaction with, willingness to repeat, and likelihood to recommend the session.
- (viii) Bacterial STI-related knowledge: 22-item scale to assess the participant's knowledge of GC, CT, and syphilis⁹⁸ for comparison with the baseline survey responses.

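### The self-efficacy outcome compares item sets that are only similar, so it may mix change in self-efficacy with the gap between expected and experienced ease

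*Combined protocol and SAP*

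**What the plan says.** **Baseline.** Section 3.a, item (vii), carries the self-efficacy label and consists of "5-point Likert items to assess the participant's perceived ease of self-collecting each type of specimen". The survey comes before the pre-test session (Section 3.b), and the collection box is shipped only after that session is completed (Section 3.c).

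**Follow-up.** For urine, throat swab, rectal swab and finger-stick blood in turn, Section 3.e, items (ii)-(v), lists "5-point Likert items to assess the participant's experience with, willingness to repeat, and likelihood to recommend self-collection". No entry in that list is labelled self-efficacy. Only the knowledge scale, item (viii), is marked for comparison with baseline. The survey goes to all 75 fully enrolled participants, "regardless of their level of engagement in the pre-test session, specimen return for bacterial STI testing, and the post-test session".

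**Analysis.** In Ame00143150, the amended Section 1.b bases the self-efficacy comparison on "similar sets of questions on the ease or difficulty of self-collecting each specimen". The amended Section 5.a, secondary IMB outcome (iii), repeats this as "comparing responses to similar sets of four 5-point Likert items included in the baseline survey and the satisfaction survey" and adds: "Response values will be summed to obtain separate total scores ranging from 4-20". The knowledge outcome two entries earlier is worded differently: it is assessed by "comparing responses to the same set of 22 items included in the baseline survey and the satisfaction survey".

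**The concern.** A before-after difference measures change in a construct only if the same thing is asked both times. The plan does this for knowledge. For self-efficacy it promises only similarity, and the one place that describes the follow-up items presents them as ratings of an experience. If those items rate a collection already done, a man can appear to gain self-efficacy because the swab was easier than he feared, or to lose it because the finger-stick was harder than he guessed. Pairing the data within participants does not separate these components. Nor does confining the analysis to descriptive summaries, because the problem is what the score means and not how its uncertainty is handled.

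A second difficulty follows from who is asked. Everyone receives the satisfaction survey, specimen return is voluntary, and a man who does not complete the pre-test session is never sent a box. Such a man has no collection to rate, and the plan gives no scoring rule for him or for a man who collected only some specimens.

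Raising confidence in self-collection is a stated aim of the pre-test session, and this is one of three measures of the intervention's potential impact on the IMB constructs. A mislabelled difference could therefore mislead those refining the intervention for the future study.

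**Working it through.** **1. The plan's own figure.** Four items coded 1 to 5 (the coding is implied by the range) give a minimum of 4 × 1 = 4 and a maximum of 4 × 5 = 20. The stated 4-20 range reproduces, and the span is 20 − 4 = 16.

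**2. The two instruments side by side.**

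| | Baseline | Follow-up |
|---|---|---|
| Label in survey list | Self-efficacy | Experience of self-collection |
| Content in survey list | Perceived ease, by specimen | Experience, willingness to repeat, likelihood to recommend, by specimen |
| Timing | Before session and kit | After intervention delivery |
| Content in amended 1.b | Ease or difficulty | Ease or difficulty |
| Relation between sets | Similar | Similar |

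The first three rows suggest different questions. The fourth shows the same subject matter. Item wording and tense are not given for either set.

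**3. Size of a spurious shift.** Assume that self-efficacy does not change and that experienced ease differs from expected ease by d_j points on specimen item j. The total then changes by d_1 + d_2 + d_3 + d_4. The documents give no value for d_j, so 0.5 to 1 point is an assumption.

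- All four in the same direction: 4 × 0.5 = 2 points (2/16 = 12.5% of the span) up to 4 × 1 = 4 points (4/16 = 25%), with either sign.
- Three one way and one the other, equal size: (3 − 1) × 0.5 = 1 point (6.25%) up to (3 − 1) × 1 = 2 points (12.5%).
- Two up and two down, equal size: 0.

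The illustrative range therefore runs from 0 to 4 points in absolute value.

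**4. Incomplete collection.** If a follow-up item can be answered only for a specimen actually collected, m specimens give a sum between m and 5m:

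| Specimens collected | Attainable sum |
|---|---|
| 0 | none |
| 1 | 1-5 |
| 2 | 2-10 |
| 3 | 3-15 |
| 4 | 4-20 |

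Only the last row has the stated range, yet sums from two or three specimens can fall inside 4-20 and pass for low scores. For example, a man who answers 4 on every item totals 4 × 4 = 16 at baseline. If he collects three specimens and the blank is left out of the sum, he totals 3 × 4 = 12, an apparent fall of 4 points with no answer changed.

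The share of men collecting all four specimens is not given. At an assumed 50%, 75% or 90%, the number with a complete follow-up set is 75 × 0.50 = 37.5 (about 38), 75 × 0.75 = 56.25 (about 56) or 75 × 0.90 = 67.5 (about 68), before any survey non-response.

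**The case against.** The strongest reply is that the questionnaires are not in the documents. The amended Section 1.b describes both sets alike, as covering ease or difficulty, so a follow-up item worded prospectively is not excluded. The list in Section 3.e is also only a summary. The amended Section 5.a scores a satisfaction item for each specimen, for example, although the list names satisfaction only for the two sessions. Experience may therefore be an umbrella term. This stands: the mismatch follows from how the items are described and has not been shown from their wording.

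A reader might go further and infer that the difference is purely expectation error and contains no change in self-efficacy. The documents do not support that. The plan itself measures self-efficacy as perceived ease, and the pre-test session demonstrates the kit and reviews the steps in order to raise it. Easier collection may thus partly reflect skill or confidence gained. Nor is baseline ease purely anticipated for everyone, because the baseline survey asks about earlier use of home STI tests and some men may already have self-collected.

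Two further points stand. A shift of 2 to 4 points requires all four specimens to move together, and opposite movements cancel. Scoring partial collectors is a missing-data matter that does not itself prove a difference in construct, although it makes the follow-up total harder to interpret.

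The reply does not remove the ambiguity. The plan commits to identical items for knowledge and not for self-efficacy, gives no reason, and lists no follow-up measure under that name.

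**Conclusion.** The concern holds in a limited form. As described, the two item sets may not measure the same thing. The difference in totals may therefore mix change in self-efficacy with the gap between expected and experienced ease, and it should not be reported as improvement in self-efficacy unless the items are shown to match. Men who collected none or only some of the specimens may have no valid follow-up total.

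The size is unknown. On an assumed gap of 0.5 to 1 point per item with self-efficacy unchanged, the distortion is anywhere from 0 to 4 points of the 16-point span, with either sign. The 12.5% to 25% figures are the case where all four specimens shift together and are not an expected effect. The conclusion rests on the survey descriptions, since item wording is not shown.

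The outcome is secondary, is summarised without inference, and has no stated decision rule attached, so the impact is limited. The correction is cheap and should be made.

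**What to change.** 1. State the wording of both item sets in the plan.
2. In the satisfaction survey, repeat the wording of baseline item (vii) for each of the four specimens, framed prospectively (how easy it would be to self-collect this specimen again or in future). Ask it of every participant, whether or not he collected. Base outcome (iii) only on these identical items. This gives non-collectors and partial collectors an answerable set of four and preserves the 4-20 range.
3. Report experienced ease or difficulty separately, by specimen, among men who collected that specimen.
4. For surveys already returned without identical items, report anticipated versus experienced ease among collectors, and do not label it improvement in self-efficacy. State that a total is formed only when all four items are answered, or give the rule used instead.

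The cost is four extra 5-point items and a survey amendment, or only a change of label where the survey can no longer be altered. The downside is that surveys already returned lack the repeated items, so outcome (iii) in its proper form would cover only later respondents. If the existing follow-up items turn out to be identical and prospective, the plan need only say so.
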